## 7.4 Safety

### 7.4.1 Carbohydrate metabolism

Fasting plasma glucose and insulin levels will be measured at baseline, at 6 and 12 months, then annually during GH treatment, and at the end of treatment.

After an overnight fast, venous blood samples will be taken to assess fasting glucose and insulin levels. Insulin resistance will be estimated using both the homeostasis model assessment (HOMA) (Matthews et al 1985) and quantitative insulin sensitivity check index (QUICKI) (Katz et al 2000, WHO 2002).

$$\text{HOMA} = \frac{\text{fasting insulin } (\mu\text{U/ml}) \times \text{fasting glucose } (\text{mg/dl})}{405 *}$$

\*use constant 22.5 instead of 405 if glucose concentration is reported in mmol/L

$$\text{QUICKI} = \frac{1}{\log \text{fasting insulin } (\mu\text{U/ml}) + \log \text{fasting glucose } (\text{mg/dl})}$$

Glycosylated haemoglobin (HbA1C) will be measured at baseline, at 6 and 12 months and then annually during GH treatment, and at the end of treatment.

An oral glucose tolerance test (OGTT) will be performed at baseline, at 6 and 12 months and then annually during GH treatment, and at the end of treatment.

The OGTT is a provocation test to examine the efficiency of the body to metabolise glucose. The OGTT provides information on latent diabetes states. The OGTT will be carried out according to WHO criteria (2002). After 3 days of an unrestricted, carbohydrate-rich diet, and after overnight fasting, 1.75 grams of glucose per kg body weight (up to a maximum of 75 g) will be administered orally after being dissolved in 250-300 ml of water. Blood samples will be taken 10 minutes before, and 120 minutes after the glucose load. Diabetes mellitus is defined by  $\geq 200$  mg/dl or  $\geq 11.1$  mmol/L blood glucose after 120 minutes.

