#### **4.6.2.2 Carbohydrate metabolism**

Fasting plasma glucose, insulin levels and glycosylated hemoglobin (HbA1C) are measured at baseline (start of treatment), at 6 and 12 months, then annually during GH treatment, and at the end of treatment. An OGTT is performed at the same time points.

The OGTT is a provocation test to examine the efficiency of the body to metabolize glucose. The OGTT provides information on latent diabetes states.

Insulin resistance will be estimated using both the homeostasis model assessment (HOMA) and quantitative insulin sensitivity check index (QUICKI)

$$\text{HOMA} = \frac{\text{fasting insulin } (\mu\text{U/ml}) \times \text{fasting glucose } (\text{mg/dl})}{405^*}$$

\*use constant 22.5 instead of 405 if glucose concentration is reported in mmol/L

$$\text{QUICKI} = \frac{1}{\log \text{fasting insulin } (\mu\text{U/ml}) + \log \text{fasting glucose } (\text{mg/dl})}$$

Carbohydrate metabolism data will be listed per parameter and will include: visit, sample date, parameter result, reference range, outside reference range indicator, clinical significance and a column containing comments.

Carbohydrate metabolism data as well as HOMA and QUICKI scores will be summarized by parameters and visit for the SAF for absolute values, and absolute and relative changes from baseline.

Shift tables for changes in the reference range classification as compared to baseline will be prepared for fasting plasma glucose, fasting insulin levels and HbA1C. The categories "low", "normal", "high" and "Missing" will be used in the shift tables. Shifts between categories will be displayed using absolute counts. Percentages will be provided per baseline category (without considering missings) for each post-baseline category, and based on all non-missing patients for total line/column.

In addition number and percentage of patients with DM and without DM finding will be presented. Patients fulfilling any criteria for DM given in section 4.5 will be regarded as patients with DM, patients not fulfilling any criteria on at least one visit will be considered as patients without DM finding.

Implausible insulin or glucose values will be excluded, i.e. Glucose values below 0.1 mmol/L and insulin values below 0.1 pmol/L will not be used for the calculation of HOMA and QUICKI.

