#### **4.6.2.5 Conversion factors for laboratory parameters**

In order to harmonize laboratory results by using the same units, some laboratory results will be converted. Corresponding conversion factors will be displayed in a table.

All glucose values will be converted to values given in mmol/l (if possible). To omit problems in assessment of impaired glucose tolerance (IGT) and impaired fasting glucose (IFG) caused by this conversion all the converted glucose values will be rounded to one digit before assessing IGT and IFG.

If albumin is given in %, the respective values will be converted to g/l using total protein values.

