**TABLE 14.3-3.7 SUMMARY OF PATIENTS WITH LABORATORY PARAMETERS FULLFILING THE DEFINITION OF DIABETES MELLITUS (DM) (SAF)**

	Total	Number of patients with DM (%)	Number of patients without DM finding (%)
Female	XXX	XX (XX.X%)	XX (XX.X%)
Male	XXX	XX (XX.X%)	XX (XX.X%)
Total	XXX	XX (XX.X%)	XX (XX.X%)

DM is defined as fulfilment of one of the following criteria:

1. FPG  $\geq 126$  mg/dl ( $\geq 7.0$  mmol/l) during safety lab assessment or as -10min value of OGTT
2. 2-h plasma glucose  $\geq 200$  mg/dl ( $\geq 11.1$  mmol/l) during OGTT
3. HbA1C  $\geq 6.5\%$

Patients not fulfilling at least one criteria on at least one visit are considered as patients without DM finding

**TABLE 14.3-3.7.1 SUMMARY OF OVERWEIGHT\* PATIENTS AT BASELINE WITH LABORATORY PARAMETERS FULLFILING THE DEFINITION OF DIABETES MELLITUS (DM) (SAF)**

Sex	Total	Number of patients with DM (%)	Number of patients without DM finding (%)
Female	XXX	XX (XX.X%)	XX (XX.X%)
Male	XXX	XX (XX.X%)	XX (XX.X%)
Total	XXX	XX (XX.X%)	XX (XX.X%)

\* Defined by international cut off points for BMI for overweight by sex and age at baseline. The cut-off point is defined by the percentile that passes through BMI at 25 kg/m^2 at age 18.

DM is defined as fulfilment of one of the following criteria:

1. FPG  $\geq 126$  mg/dl ( $\geq 7.0$  mmol/l) during OGTT or safety lab assessment
2. 2-h plasma glucose  $\geq 200$  mg/dl ( $\geq 11.1$  mmol/l) during OGTT
3. HbA1C  $\geq 6.5\%$

Patients not fulfilling at least one criteria on at least one visit are considered as patients without DM finding

**TABLE 14.3-3.8 SUMMARY OF PATIENTS WITH LABORATORY PARAMETERS FULLFILING THE DEFINITION OF IMPAIRED GLUCOSE TOLERANCE (IGT) (SAF)**

	Total	Number of patients with IGT (%)	Number of patients without IGT finding (%)
Female	XXX	XX (XX.X%)	XX (XX.X%)
Male	XXX	XX (XX.X%)	XX (XX.X%)
Total	XXX	XX (XX.X%)	XX (XX.X%)

IGT is defined as fulfilment of all of the following criteria:

1. FPG < 126 mg/dl (<7.0 mmol/l) during OGTT or safety lab assessment
2. 2-h plasma glucose between 140 – 200 mg/dl (≥7.8 and <11.1 mmol/l) during OGTT

Patients not fulfilling all criteria on at least one visit are considered as patients without IGT finding

**TABLE 14.3-3.9 SUMMARY OF PATIENTS WITH LABORATORY PARAMETERS FULLFILING THE DEFINITION OF IMPAIRED FASTING GLUCOSE (IFG) (SAF)**

	Total	Number of patients with IFG (%)	Number of patients without IFG finding (%)
Female	XXX	XX (XX.X%)	XX (XX.X%)

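### The 0.1 pmol/L insulin floor for HOMA and QUICKI is too low to screen out implausible values and lies close to the curve on which QUICKI is undefined

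*SAP*

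**What the plan says.** Protocol section 7.4.1 and SAP section 4.6.2.2 estimate insulin resistance by HOMA and QUICKI. Both print QUICKI as the reciprocal of log fasting insulin in uU/ml plus log fasting glucose in mg/dl. HOMA is the product of the two divided by 405, with the instruction "use constant 22.5 instead of 405 if glucose concentration is reported in mmol/L". QUICKI has no mmol/L form.

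SAP 4.6.2.2 states an intention, "Implausible insulin or glucose values will be excluded", and then defines it: "Glucose values below 0.1 mmol/L and insulin values below 0.1 pmol/L will not be used for the calculation of HOMA and QUICKI". Values equal to the floor stay in. The SAP gives no rule for a zero or negative QUICKI denominator and no other filter for these scores.

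The outputs follow: "HOMA and QUICKI scores will be summarized by parameters and visit for the SAF for absolute values, and absolute and relative changes from baseline". Under SAP section 2.1 each summary shows mean, SD, minimum, quartiles, median and maximum. SAP section 4.6.2.5 converts glucose to mmol/l where possible and promises a table of conversion factors. Its shell (Table 14.3-2.1) shows no insulin row before it breaks off in an ellipsis.

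**The concern.** A plausibility filter should stop values that cannot be real fasting results, and above all those for which the formula misbehaves. QUICKI has a pole: as insulin times glucose falls towards 1 the index grows without bound, and below 1 it is negative. A floor near that pole admits records whose QUICKI means nothing. Such inputs are conceivable because insulin is measured by local laboratories (protocol section 7.4.6.1) and units have to be harmonised afterwards, so a unit slip could produce a very small recorded insulin.

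At stake are the means, SDs and extremes in Tables 14.3-2.8 to 14.3-2.10. HOMA and QUICKI are the only planned estimates of insulin resistance in a study set up to examine diabetogenic potential.

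**Working it through.** **Inputs from the documents**
- Insulin floor: 0.1 pmol/L (SAP 4.6.2.2). It is stated without a derivation, so there is no figure of the plan to reproduce.
- Glucose factor: 405 / 22.5 = 18.0 mg/dl per mmol/L. The diabetes thresholds agree: 126 / 7.0 = 18.0.
- Safety set: 277 (SAP Table 14.3-1.1).

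**Assumptions (not in the documents)**
- Insulin conversion k = 6.0 to 6.945 pmol/L per uU/ml.
- Log base 10. The base is not stated, but the zero of the denominator does not depend on it.
- Ordinary fasting insulin about 5 uU/ml, and 8 uU/ml later on treatment. Usual QUICKI about 0.35, as 1 / log10(8 × 90) = 0.350.
- For the effect on a summary: QUICKI mean 0.37, SD 0.04 in the other children.

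**Step 1. The floor in formula units.** 0.1 / 6.0 = 0.0167 and 0.1 / 6.945 = 0.0144 uU/ml. Against 5 uU/ml these are 300 and 347 times smaller.

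**Step 2. Where QUICKI is undefined.** The denominator is zero when (insulin / k) × glucose in mg/dl = 1. At the floor, glucose = k / 0.1 = 60.0 to 69.45 mg/dl, or 3.33 to 3.86 mmol/L. At 4.5 to 5.5 mmol/L (81 to 99 mg/dl) the zero falls at insulin = k / glucose, from 6.0 / 99 = 0.061 to 6.945 / 81 = 0.086 pmol/L. That is just below the floor, so the pole itself is excluded there.

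**Step 3. QUICKI for admitted records**, 1 / log10(insulin / k × 18 × glucose in mmol/L):

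| Insulin (pmol/L) | Glucose (mmol/L) | k = 6.0 | k = 6.945 |
|---|---|---|---|
| 0.1 | 5.0 | 5.7 | 8.9 |
| 0.1 | 4.7 | 6.7 | 11.7 |
| 0.5 | 4.7 | 1.18 | 1.27 |
| 1 | 4.7 | 0.87 | 0.92 |
| 3 | 4.7 | 0.61 | 0.64 |

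Worked case: 0.1 / 6.945 × 90 = 1.296; log10 = 0.1126; reciprocal 8.88. At glucose 3.3 mmol/L (59.4 mg/dl) the product is 0.99 or 0.855, both below 1, so QUICKI is negative and the rule still admits the record.

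**Step 4. One such record among 277.** New mean = (276 × 0.37 + q) / 277. New variance = [275 × 0.04² + (276/277)(q − 0.37)²] / 276. For q = 5.68 the mean is 0.389 and the SD 0.32. For q = 8.88 the mean is 0.401 and the SD 0.51. With 250 children and q = 8.88 the SD is 0.54. The SD without the record is 0.04.

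**Step 5. Relative HOMA.** If the floor value is the baseline and later insulin is 8 uU/ml at unchanged glucose, the child's change is (8 / 0.0167 − 1) to (8 / 0.0144 − 1), that is +47,900% to about +55,500%. Divided by 277, this adds roughly 173 to 200 percentage points to the mean. In a simulated visit of 277 with glucose varying (mean about 4.7 mmol/L, SD 0.4) and baseline insulin median 5 uU/ml (log-SD 0.5), the mean relative change moved from 107% to 287% to 316% and the SD from 161 to about 3,000 to 3,470; the median stayed at 67%. The same record at a later visit can give at worst −100% and moved the mean only from 107.1% to 106.4%.

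**The case against.** The case for leaving the rule alone has real parts.

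- A reader might infer that 0.1 pmol/L is itself the point of division by zero. It is not. The zero is a curve, and at glucose of 4.5 to 5.5 mmol/L the floor does exclude it. Extreme or negative scores need insulin near the floor and low glucose in one record. This stands. What remains is that the finite values admitted at ordinary glucose are still absurd.
- The effect fades quickly: at 1 pmol/L and glucose 4.7 mmol/L QUICKI is about 0.9. This also stands.
- A reader might infer that the summaries as a whole become unusable. Medians and quartiles are planned and hold (the simulated QUICKI median moved from 0.3832 to 0.3836), a QUICKI near 9 would show as the maximum, and SAP section 5.5 lists insulin and every score. Listing exposes the record but does not say what to do with it.
- The units might be read as an error in the plan. The formulas print their units and a conversion table is promised, so using mmol/L glucose in QUICKI (0.62 in place of 0.35) would be a programming mistake. Only a clarification is warranted.
- SAP section 4.7 already uses the number without its sign for results reported as below a limit. It names hematology, blood chemistry and thyroid. The SAP's blood chemistry list omits insulin, although the protocol places insulin under biochemistry, so coverage is unclear.
- A much higher cut-off could bias the comparison. Protocol section 1.2.4 reports that growth hormone raises fasting insulin, so genuine low values may cluster at baseline, and dropping them would raise baseline HOMA and shrink the change. This stands and shapes the fix.

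**Conclusion.** The point holds as a weakness of a stated rule: the floor does not do the job the SAP gives it. One admitted record at 0.1 pmol/L with glucose 5.0 mmol/L would give QUICKI 5.7 to 8.9 and raise that visit's SD from 0.04 to between 0.32 and 0.51 among 277 children. As a baseline value it would also put that child's relative HOMA change near 50,000% at every later visit.

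These sizes rest on the assumed insulin conversion and the assumed typical values. The documents do not show that any such record exists; local laboratories make a unit slip possible, which is not evidence of one. Nor is the primary endpoint touched: diabetes is defined in SAP section 4.5 from fasting glucose, 2-hour glucose and HbA1c, and neither index is named among the endpoints in SAP section 2.3. The point is worth correcting because the correction is cheap and can be made before the final analysis.

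**What to change.** In SAP 4.6.2.2, fixed before the final analysis:

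1. Replace the 0.1 pmol/L floor with one tied to the local assays' detection limits. Set results reported below a limit to that limit, and say explicitly that the SAP 4.7 convention applies to insulin.
2. Query recorded values below any plausible detection limit as possible unit errors. If unresolved, exclude them from both indices, list them, and show the HOMA and QUICKI summaries with and without them, because genuine low values may cluster at baseline.
3. Compute no QUICKI when insulin (uU/ml) times glucose (mg/dl) is 1 or less.
4. As a minor clarification, state that QUICKI uses glucose in mg/dl after the harmonisation in 4.6.2.5, and add the insulin factor to Table 14.3-2.1.

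The cost is a few lines of SAP text, the collection of detection limits from the laboratories, one filter in the derivation program and an extra run of the summaries. The downside is that a few records are set aside and listed.

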#### **4.6.2.3 Vital signs**

Vital signs are collected at all visits.

The vital signs data include: date of examination, systolic blood pressure, diastolic blood pressure and pulse rate.

These data will be summarized by parameters and visit.

#### **4.6.2.4 Physical examination**

A thorough physical examination is performed at all visits.

The frequency of normal and abnormal evaluations and parameters not evaluated will be summarized for each physical examination system by visit. Shift table for normal / abnormal findings will be presented by body system for each visit versus baseline. The specification for other body systems will be reviewed by the sponsor. If this review identified that the entry does not belong to an other body system but to a body system already given in the CRF, the entry will be considered for the existing body system.

Weight, BMI and BMI SDS will be summarized by visit for the SAF. For details regarding BMI SDS calculation see Appendix C.

#### **4.6.2.5 Conversion factors for laboratory parameters**

In order to harmonize laboratory results by using the same units, some laboratory results will be converted. Corresponding conversion factors will be displayed in a table.

All glucose values will be converted to values given in mmol/l (if possible). To omit problems in assessment of impaired glucose tolerance (IGT) and impaired fasting glucose (IFG) caused by this conversion all the converted glucose values will be rounded to one digit before assessing IGT and IFG.

If albumin is given in %, the respective values will be converted to g/l using total protein values.

#### **4.6.2.6 Hematology**

Hematology data are collected at baseline (start of treatment), at 6 and 12 months, then annually during GH treatment, and at the end of treatment.

Hematology data include: visit, sample date, parameter result, reference range, outside reference range indicator, clinical significance and a column containing comments. The parameters included in the hematology data are: hemoglobin, hematocrit, white blood cell count (total and differential) (WBC), red blood cell count (RBC), platelet count, mean cell volume (MCV), mean cell hemoglobin (MCH), mean cell hemoglobin concentration (MCHC), erythrocyte sedimentation rate (ESR).

Hematology data will be summarized by parameters and visit.

#### **4.6.2.7 Blood chemistry**

Blood chemistry data are measured at baseline (start of treatment), at 6 and 12 months, then annually during GH treatment, and at the end of treatment.

Blood chemistry data include: visit, sample date, parameter result, reference range, outside reference range indicator, clinical significance and a column containing comments. The blood chemistry parameters are creatinine, urea, aspartate aminotransferase (SGOT/AST), alanine aminotransferase (SGPT/ALT), gamma-glutamyltransferase (gamma-GT), alkaline phosphatase, total bilirubin, albumin, total protein, HDL, LDL, sodium, potassium, chloride, uric acid, total cholesterol, triglycerides, calcium, phosphorus.

Blood chemistry will be summarized by parameters and visit for the SAF. Thyroid panel

Thyroid panel data are will be measured at baseline (start of treatment), at 6 and 12 months, then annually during GH treatment, and at the end of treatment.

Thyroid panel data include: visit, sample date, parameter result, reference range, outside reference range indicator, clinical significance and a column containing comments. The thyroid panel parameters are free thyroxine (fT4) and thyroid stimulating hormone (TSH).

Thyroid panel data will be summarized by parameters and visit.

Shift tables for changes in the reference range classification as compared to baseline will be provided for each parameter. The categories "low", "normal", "high" and "Missing" will be used in the shift tables. Shifts between categories will be displayed using absolute counts. Percentages will be provided per baseline category (without considering missings) for each post-baseline category, and based on all non-missing patients for total line/column.

#### **4.6.2.8 Urinalysis**

Urinalysis data are collected at baseline (start of treatment), at 6 and 12 months, then annually during GH treatment, and at the end of treatment.

The urinalysis data include: visit, sample date, parameter result, clinical significance and a column containing comments. The parameters included in the urinalysis data are pH, glucose, ketones, bilirubin, protein.

pH values will be summarized by visit.

All remaining urinalysis parameters will be presented as shift tables comparing baseline to post-baseline values. The categories "+", "++", "+++", "++++" and "Missing" will be used in the shift tables. Shifts between categories will be displayed using absolute counts. Percentages will be provided per baseline category (without considering missings) for each post-baseline category, and based on all non-missing patients for total line/column.

#### **4.6.3 Immunogenicity**

All patients with a positive ADA result at any time during the study will be listed individually.

Tests for anti-rhGH antibodies were performed at baseline, at 3, 6, 9, 12 18 and 24 months, then annually during Omnitrope treatment and the end of treatment. As per protocol amendment 3, the anti HCP testing should be stopped after the amendment became effective in the respective country. Therefore, all HCP results since V01 will be presented up to the Visits occurred until the amendment 3 became effective. Number and percentage of patients with positive test for anti-hGH antibodies and anti-HCP antibodies will be provided by visit and overall (for anti-HCP antibodies).

In addition summary tables and figures for H SDS and HV SDS will be presented for patients with and without positive anti-rhGH antibody test.

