#### **6.5.3 Treatment duration**

Omnitrope® treatment will continue until final height is reached. Treatment should be discontinued after the first year of treatment if the height velocity SDS is below +1 (see also 6.5.9 Study drug discontinuation).

A standardized controlled procedure for the calculation of the treatment response (“Treatment Response Control Fax”) was implemented.

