### **6.5.9 Study drug discontinuation**

Treatment can be terminated at any time, at the discretion of the investigator or the Sponsor, or at the patient's request, in the event of an AE or due to treatment failure.

Study drug treatment has to be discontinued in the following cases during treatment period:

- Occurrence of overt diabetes mellitus; defined as fasting blood glucose  $\geq 126$  mg/dl or  $\geq 7.0$  mmol/l and abnormal findings in OGTT defined by  $\geq 200$  mg/dl or  $\geq 11.1$  mmol/l after 120 minutes. For further instruction see appendix
- Requirement of an increase of the recommended dose to obtain increased growth velocity
- Renal transplantation
- Diagnosis of benign intracranial hypertension
- Malignancy
- Pregnancy
- Withdrawal of informed consent
- Treatment failure

Treatment failure is defined as: Inadequate response to treatment, e.g. height velocity standard deviation score (HVSDS) below +1 in the first year.

Furthermore a standardized controlled procedure for the calculation of the treatment response (via "Treatment Response Control Fax") was implemented (see also 6.5.3 treatment duration) to ensure a unified flawless computation and to authorize treatment continuation, if applicable (managed by Data Management at Metronomia). In case the Investigator does not agree with the assessment by Data Management, Sandoz is informed and initiates the re-assessment of the treatment response data via an independent specialist reader.

Patients who are withdrawn from the study before completing at least one year of treatment with Omnitrope® will be replaced.

Study drug must be discontinued if the investigator concludes that continuation would result in significant safety risk for that patient and in the event of pregnancy.

Patients who discontinue study drug before completing the study should not be considered withdrawn from the study and should be scheduled for a final visit as soon as possible, at which time all of the assessments for the final visit will be performed.

A Study Drug Discontinuation form should be completed, giving the date and reason for stopping the study drug. All patients who discontinue study drug, including those who refuse to return for a final visit, will be contacted for safety evaluations during the 4 weeks following the last dose of the study drug.

Patients who discontinued this study for any reason will not be able to re-enter the study.

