#### **10.4.2 Immunogenicity**

Subjects will be screened for anti-rhGH antibodies (ABs) at baseline, at 3, 6, 9, 12, 18 and 24 months, then annually during treatment, and at the end of treatment. For each time point the number and percentage of patients with anti-rhGH antibodies (ABs) will be tabulated.

Antibody-induced lack or loss of efficacy will be examined by comparing height outcome data between antibody-positive and antibody-negative subjects.

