**TABLE 14.2-1.3.3 SUMMARY OF HSDS BY COMPLETERS, TOTAL, VISIT AND INITIAL TREATMENT (FAS)**

See shell for TABLE 14.2-1.1.3 SUMMARY OF HEIGHT BY COMPLETERS, TOTAL, VISIT AND INITIAL TREATMENT (FAS).

Programming note: Please add one column 'Status' (value: Completers, Total) before column Visit.

**TABLE 14.2-1.3.4 SUMMARY OF HSDS BY COMPLETERS, TOTAL, AND VISIT FOR PATIENTS WITH AND WITHOUT POSITIVE ANTI-RHGH ANTIBODIES (FAS)**

See shell for TABLE 14.2-1.1.2 SUMMARY OF HEIGHT BY COMPLETERS, TOTAL, VISIT AND SEX (FAS).

Programming note: Present patient with and without positive anti-rhGH antibodies instead of sex. Please add one column 'Status' (value: Completers, Total) before column Visit.

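### The antibody growth comparison has no as-of-visit rule for antibody status, so a later positive test can set a child's group at earlier visits and blur or hide a loss of efficacy

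*SAP*

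**What the plan says.** Protocol 10.4.2 gives the purpose: "Antibody-induced lack or loss of efficacy will be examined by comparing height outcome data between antibody-positive and antibody-negative subjects". Protocol 7.4.2 says the same.

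SAP 4.6.3 carries this out with summary tables and figures of H SDS and HV SDS "presented for patients with and without positive anti-rhGH antibody test". The note for Table 14.2-1.3.4 reuses the shell of the height table by sex: "Present patient with and without positive anti-rhGH antibodies instead of sex". Tables 14.2-1.7.4 and 14.2-1.9.4 carry the same instruction for the two versions of HV SDS. All three are by visit, with rows for Completers and Total. Figures 14.2-1.12.1, 14.2-1.14.1 and 14.2-1.15.1 show the same contrast without the completer split.

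The only time reference for positivity belongs to a listing: "All patients with a positive ADA result at any time during the study will be listed individually". No rule covers baseline-positive or transiently positive children.

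Testing depends on staying on treatment: "Tests for anti-rhGH antibodies were performed at baseline, at 3, 6, 9, 12 18 and 24 months, then annually during Omnitrope treatment", and again at its end. Staying depends on response. Protocol 6.5.3 says "Treatment should be discontinued after the first year of treatment if the height velocity SDS is below +1", and Protocol 6.5.9 gives as its example of treatment failure "Inadequate response to treatment, e.g. height velocity standard deviation score (HVSDS) below +1 in the first year".

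**The concern.** Sex is known at baseline and never changes; antibody status is learned over years. If status simply takes the place of sex in a by-visit table, a child first positive in year 5 sits in the positive row at month 12, when the child was still negative. Two things follow.

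- Pre-conversion growth is counted as antibody-positive growth, which dilutes any real loss.
- First-year growth helps decide how many tests a child gets. Poor responders who stop at month 12 collect in the negative group, which makes the positive group look better than it is.

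Both push towards reassurance. Immunogenicity is a stated purpose of the study (Protocol section 2) and part of the EMEA request (Protocol section 11), and this is the planned comparison for antibody-related lack or loss of efficacy.

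**Working it through.** The plan gives no figure for this comparison, so there is none to reproduce. The check has two parts.

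**1. Chances of being labelled positive.** The schedule is months 3, 6, 9, 12, 18 and 24, then annually. A child stopped at month 12 has k = 4 scheduled post-baseline tests. Protocol, Study status, gives last enrolment on 29-Apr-2010 and 32 children still treated on 31-Dec-2019, which is about 9.7 years. Such a child has 6 tests to month 24 plus 7 annual tests (months 36 to 108), so k = 13. The end-of-treatment test is not counted. With per-test probability p (assumed), P(ever positive) = 1 − (1 − p)^k:

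| p | k = 4 | k = 13 |
|---|---|---|
| 0.5% | 2.0% | 6.3% |
| 1% | 1 − 0.99^4 = 3.9% | 1 − 0.99^13 = 12.2% |
| 2% | 7.8% | 23.1% |
| 5% | 18.5% | 48.7% |

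**2. Effect on the month-12 comparison.** Simulation, 1,000,000 children per scenario. All inputs except the test schedule and the +1 threshold are assumptions:

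- month-12 HVSDS normal, mean 2.5 to 3, SD 1.5 to 2, so 9% to 23% fall below +1;
- every child below +1 stops at month 12; the others have a planned stay of 3 to 11 years;
- other drop-out of 5% per year, unrelated to growth;
- p from 1% to 5% per test, either constant or falling to one tenth after year 1;
- where a true effect is assumed, a loss of 1.0 SDS in children positive by month 9.

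Difference in month-12 HVSDS, positive minus negative:

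| Scenario | Rows | Ever vs never | Status known by month 12 |
|---|---|---|---|
| No effect, constant conversion | Total | about +0.15 to +0.55 | −0.01 to +0.01 |
| No effect, mostly year 1 | Total | +0.03 to +0.10 | about 0 |
| No effect, constant conversion | Completers | −0.01 to +0.01 | about 0 |
| Loss of 1.0, constant conversion | Total | −0.19 to +0.11 | about −0.75 to −0.77 |
| Loss of 1.0, mostly year 1 | Total | about −0.6 to −0.66 | about −0.75 |
| Loss of 1.0, constant conversion | Completers | about −0.13 to −0.19 | −0.35 to −0.46 |

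With no effect, the Total rows at month 24 also show about 0, because the first-year failures have left.

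Status known by month 12 gives about −0.75 rather than −1.0 because it includes children first positive at month 12 itself, whose growth to that point was unaffected. Comparing children positive before month 12 with the rest gives about −1.0. In Completers the figure is smaller still because children pushed below +1 by the loss have stopped. A better grouping variable does not repair that selection.

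A simpler run without other drop-out (mean 2.5 or 3.5, SD 2, p of 1% or 2%) shows the mechanism. At constant p = 1% and no effect, 10.0% of responders but 3.9% of year-1 failures are labelled positive. Across its constant-rate, no-effect scenarios, 53% to 58% of the ever-positive group convert after month 12.

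**The case against.** **The fixed grouping is inferred.** The SAP never says ever positive. The wording about any time during the study belongs to the listing, the note about sex may only mean that a shell is reused, and Table 14.3-3.10 already tabulates results by visit. This stands as a limit on confidence. But no as-of-visit rule exists, so the programmer must choose, and the wording points to one group per child.

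**The spurious benefit is local.** It appears in the Total rows and the unsplit figures at month 12. It is absent from Completers and, with later drop-out unrelated to growth, from later visits. This stands. The dilution of a true loss in Completers remains.

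**The size depends on when children convert.** This stands. Testing is densest in year 1. If conversion is too, the spurious benefit is small and most of a true loss stays visible.

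**The stopping rule is not absolute.** The protocol says treatment should stop, gives the threshold as an example, and allows independent re-assessment. SAP Table 14.1-16 has a line for patients who met withdrawal criteria but were not discontinued. If only half of the children below +1 stop, a benefit of +0.42 falls to about +0.19.

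**Little hangs on it.** The comparison is descriptive, with no test or decision rule, and positive children are listed individually. At p = 1%, about 277 × 0.039 = 11 children are positive by month 12. With SD 1.5 to 2, the standard error of the difference is SD × √(1/11 + 1/266), or 0.46 to 0.62 SDS, larger than most of the biases above. This lowers the priority. However, Listing 16.2.6.6 shows antibody results, not a growth comparison, and noise is no reason to keep a grouping that leans one way.

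**Conclusion.** The gap is real and worth closing; confidence is medium. As written, the plan gives no as-of-visit rule, and its natural reading lets future positivity define past groups while the year-1 rule gives poor responders fewer tests.

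Under the stated assumptions, the spurious month-12 benefit in Total runs from about +0.15 to +0.55 HVSDS (constant conversion) down to +0.03 to +0.10 (mostly year 1), and is smaller if the stopping rule is not always applied. In Completers there is no spurious benefit, but with constant conversion a 1.0 SDS loss shows as about −0.13 to −0.19, against −0.35 to −0.46 with status known by month 12.

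A reader might infer that the comparison is bound to hide a loss of efficacy at every visit. The documents do not support that: they give neither the rate nor the timing of antibody conversion, the tables separate visits and completers, and with mostly early conversion most of a true loss still shows in Total.

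**What to change.** In SAP 4.6.3, in Tables 14.2-1.3.4, 14.2-1.7.4 and 14.2-1.9.4, and in Figures 14.2-1.12.1, 14.2-1.14.1 and 14.2-1.15.1, define antibody status at each visit as at least one positive post-baseline anti-rhGH test at or before that visit. Replace the note about sex with this definition.

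Optionally, for positive children, show growth before and after the first positive test.

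The cost is SAP wording and one derived grouping variable; no new data are needed. Positive groups become smaller, especially at early visits, and their means less precise.
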